Eligibility: Participants must have a history of self-report injection opioid use in the past 6 months, participate in SSPs, be HIV negative, willing to take bup/nx and PrEP for 6 months, have no medical contraindications for these medications such as history of renal failure or bone diseases, not be pregnant and be 18 years or older. In addition, participants must not currently be taking PrEP or any form of MOUD, and have either a history of sharing injection or drug preparation equipment or risk of sexual acquisition of HIV (such as engaging in sex work or men who have sex with men) in the past 6 months.

Exclusion criteria: Positive pregnancy test, positive HIV test at enrollment, altered mental status in which participant cannot sign a consent form, or evidence of renal failure (estimated creatinine clearance <60 mL/min) will be cause for exclusion from the study. Although hepatitis B is not necessarily a contraindication to PrEP use, participants who are hepatitis B surface antigen positive will be excluded from this study and referred to an experienced hepatitis B and PrEP provider.

In the event that a participant becomes incarcerated during the course of the study, the study team will withdraw the participant from the protocol and cease any ongoing study activities, including ongoing data collection. If a participant becomes pregnant on study, they will also be withdrawn from the study, and all efforts will be made to link the pregnant woman to PrEP and MOUD services in the community without lapse. For participants who withdraw from the study, all data already collected will be stored securely within the Duke electronic medical record.

Sample size: We plan to enroll 20 PWID (10 at each site). If a participant drops out before completing the 6 months, we will consider enrolling another participant to fill the spot. Participants will be allowed to stay on study even if they stop taking one of the paired medications.

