The total number to treat will be 20 (10 at each site) as this is a pilot/feasibility study. We will consider enrolling new participants if there is an early withdrawal.

For Objective 1, we will use descriptive statistics to describe the baseline characteristics of the sample, including their demographics, sexual and injection risk behaviors, history of substance abuse, perceptions of and interest in MOUD, and awareness of and interest in using PrEP.

For Objective 2, we will collect feasibility information such as how many times the PI and study coordinator travelled to the SSP site, how many telemedicine visits occurred per participant, how long the visits lasted, how many were rescheduled or did not happen on time. Similar information will be collected from SSP staff who participated in this program.

By the end of the study, we hope to determine the following:

1. The proportion of persons who demonstrate no or minimal opioid use

Providing comprehensive harm reduction via telemedicine for PWID using syringe services programs: a feasibility study

- a. Defined as completing Month 3 and Month 6 visits with self-reported opioid use on ≤4 days in the past month and/or 2 or more consecutive negative urine tests.
2. The proportion of persons who remain HIV negative.
 - a. Measured via negative HIV test at Month 3 and Month 6
3. Retention or persistence in care
 - a. Defined as the proportion who remain on treatment (MOUD, PrEP or both) at Month 3 and Month 6
 - b. We will also examine whether participants are more apt to remain on paired/combined therapy compared to individual treatment.

7. Reimbursement

Medical care and medications are being provided free of charge and participants will be provided with bus passes to cover all visits to the SSP (weekly for Month 1 and then monthly until end of study) and to the pharmacy. Participants will be offered additional bus passes for unscheduled visits if needed.

Description of Potential Risks

The study will provide MOUD with bup/nx and a prescription for PrEP for 6 months. At the end of study, all participants will be linked with local MOUD and PrEP clinics in Charlotte to ensure continuity of care. These clinics will be identified early in the study. If participants are leaving the area, assistance will be given to locate an appropriate clinic.

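### Does the persistence proportion in section 6, item 3a need a stated denominator, given replacements and withdrawals by rule?

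*Combined protocol and SAP*

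**What the plan says.** Section 6 (Data analysis) fixes the size: "The total number to treat will be 20 (10 at each site) as this is a pilot/feasibility study". The next sentence adds: "We will consider enrolling new participants if there is an early withdrawal". The sample size paragraph of section 5 has a parallel rule: "If a participant drops out before completing the 6 months, we will consider enrolling another participant to fill the spot".

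Persistence is part of objective (a) in section 2. Its measure is section 6, item 3a: "Defined as the proportion who remain on treatment (MOUD, PrEP or both) at Month 3 and Month 6". No denominator is named there. Item 1 is worded per person: "The proportion of persons who demonstrate no or minimal opioid use".

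Section 5 (Eligibility) provides for two withdrawals by rule. On incarceration, "the study team will withdraw the participant from the protocol and cease any ongoing study activities, including ongoing data collection". A participant who becomes pregnant is also withdrawn, and "all efforts will be made to link the pregnant woman to PrEP and MOUD services in the community without lapse". On the data of people who leave, the plan says: "For participants who withdraw from the study, all data already collected will be stored securely within the Duke electronic medical record". That is a storage rule and does not say how these people enter the analysis.

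**The concern.** A proportion needs a numerator and a denominator, and item 3a supplies only the first. Three features of the plan make the gap look more than cosmetic.

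- Replacement can take the number treated above 20, with no stated limit. If people still on treatment were divided by 20 filled places, early leavers would vanish from the denominator while their replacements entered the numerator. Retention could then only be raised.
- Leaving is related to the outcome. The section on potential risks names both incarceration and study withdrawal among the causes of abrupt bup/nx discontinuation, so dropping leavers from the count would not be neutral.
- For rule-based withdrawals, later treatment status is not collected (incarceration) or may continue outside the study (pregnancy). The plan does not say whether such a person counts as on treatment, as not on treatment, or not at all.

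At stake is the reading of one descriptive proportion that serves a stated objective, and its comparison with other programs.

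**Working it through.** **Inputs from the documents.** Planned number: 2 sites × 10 = 20, which reproduces the stated total. There is no dropout rate, retention rate, precision target, test or threshold. All retention, replacement and withdrawal figures below are therefore assumptions.

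**1. Replacement.** Let r be the true retention, q = 0.7 the share of non-retained people who leave, and f = 0.5 the share of leavers replaced (once).

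- Expected replacements: k = 20 × f × q × (1 − r). At r = 0.5 this is 20 × 0.5 × 0.7 × 0.5 = 3.5.
- Retained over 20 filled places: r + f × q × (1 − r) × r. At r = 0.5 this is 0.5 + 0.35 × 0.5 × 0.5 = 0.5875.
- Retained over everyone who started: the expectation of retained/(20 + D), where D is the number replaced, binomial among the non-retained with probability f × q = 0.35.

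| True r | Expected k | Over 20 places | Overstatement (points) | Over all who started |
|---|---|---|---|---|
| 30% | 4.9 | 37.4% | 7.4 | 30.2% |
| 50% | 3.5 | 58.8% | 8.8 | 50.3% |
| 70% | 2.1 | 77.4% | 7.4 | 70.3% |
| 80% | 1.4 | 85.6% | 5.6 | 80.2% |

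The overstatement belongs entirely to the per-place denominator. Over persons who started, the bias is at most 0.3 points.

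**2. A worked case with whole numbers.** Suppose 4 of the first 20 leave early, all are replaced, and 80% of the rest are on treatment at Month 6.

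- All treated: 16/24 = 66.7% (exact 95% CI 44.7 to 84.4)
- First 20 only: 13/20 = 65.0% (40.8 to 84.6)
- Filled places: 16/20 = 80.0% (56.3 to 94.3)
- First 20 with the leavers dropped: 13/16 = 81.3% (54.4 to 96.0)

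The two denominators that keep every person in the count differ by 66.7 − 65.0 = 1.7 points. The spread of about 16 points (81.3 − 65.0) appears only when leavers are removed from the denominator, and no passage of the plan does that.

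**3. Which denominator the text supports.** Items 1 and 2 of section 6 are proportions of persons. The wording about filling a place stands in the sample size paragraph and concerns enrolment. The sentence permitting new participants directly follows the total of 20, so the two together already mean 20 plus any replacements.

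**4. Rule-based withdrawals.** With N = 20, w people withdrawn by rule and 10 others on treatment, the proportion is 10/20 if the withdrawn count as not on treatment, 10/(20 − w) if they are excluded, and (10 + w)/20 if they count as on treatment.

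| w | Not on treatment | Excluded | On treatment |
|---|---|---|---|
| 1 | 50.0% | 52.6% | 55.0% |
| 2 | 50.0% | 55.6% | 60.0% |
| 3 | 50.0% | 58.8% | 65.0% |

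The exact 95% interval for 10/20 is 27.2% to 72.8%, which contains every entry.

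**The case for a change.** The strongest case for a change is that, in a descriptive study, the proportion is the result, so its denominator should be fixed before the data are seen. A denominator effect is also systematic, and a confidence interval around the wrong proportion does not reveal it. The gap over rule-based withdrawals exists even if nobody is replaced, and a few sentences would close it.

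Part of this stands. The omission is real, and a participant withdrawn for pregnancy but still treated in the community has no obvious place in item 3a. The rest carries less weight. The systematic effect arises only under a per-place count that the text does not state. Incarceration is less open than it seems: item 3 is headed as retention or persistence in care, and the protocol itself links incarceration to stopping bup/nx, so not retained is the ordinary reading. Item 1 requires completed Month 3 and Month 6 visits, so people who leave before either visit already fail its numerator when all persons are counted.

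Nor is a single counting rule plainly better. Counting only treatment within the study would alter item 3a, which asks about being on treatment. One pooled denominator of anyone who started either drug would mix uptake with persistence: bup/nx is grant-funded, PrEP comes through insurance or an assistance program, and a person might start only one.

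**Conclusion.** No change to the plan is needed. This is a missing detail that an analyst would fill sensibly: count everyone eligible who started treatment, including those later replaced or withdrawn; show persistence by drug; and list withdrawals by reason, with those of unknown or off-study treatment status as their own count. Given those counts, a reader can form any other denominator.

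Read this way, replacement distorts the proportion by no more than 0.3 points under the assumed leaving and replacement shares (0.7 and 0.5) and true retention of 30% to 80%. Classifying rule-based withdrawals matters by 5 points per person at N = 20. The number of such people is unknown, and with up to three of them the results stay inside the sampling error of about 20 participants. No decision rule depends on the figure. The conclusion rests on the per-person reading, and a report that divided by filled places would deserve criticism as a reporting error.

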Successful HIV prevention programs for PWID are comprehensive and should offer resources that are accessible and acceptable to the target population. Along with SSPs, these resources include medications such as daily oral pre-exposure prophylaxis (PrEP) with tenofovir/emtricitabine, and combination buprenorphine and naloxone (bup/nx) for opioid use disorder. PrEP has been proven effective for reducing HIV acquisition among PWID [1, 8]. Similarly, medication for opioid use disorder (MOUD) with bup/nx has been shown to significantly reduce cravings, overdoses and death [9]. In addition, because bup/nx reduces cravings, it can result in decreased injection drug use and needle sharing, which decreases the risk for drug-related HIV risk behaviors [10]. While both PrEP and MOUD are FDA approved – they remain underutilized, particularly among people who use drugs, for a variety of reasons including lack of awareness, cost, and lack of providers and/or access [11-14].

Providing PrEP and MOUD via SSPs represents one way to reach PWID, a particularly difficult to reach population. In 2018 we collected primary data from PWID attending SSPs, many of whom were at risk for HIV. Participants reported that they would be interested and willing to take PrEP and would prefer to access PrEP at SSPs (versus going to a medical clinic or health department). Building on this preliminary research, we will conduct a feasibility study in which we will provide both PrEP and MOUD for PWID utilizing SSPs in New Hanover and Mecklenburg counties. To facilitate access to care, telemedicine will be used for follow-up visits. Prior studies have shown no difference in outcomes between patients receiving opioid use disorder treatment through telemedicine or from face to face encounters [15, 16]. Similarly, there have been successful strategies for telemedicine-delivered PrEP [17].

P1

Providing comprehensive harm reduction via telemedicine for PWID using syringe services programs: a feasibility study

Given that the national opioid epidemic continues to escalate with alarming consequences, including heightened risk of new HIV infections, we think there is a critical need to identify novel ways to provide harm reduction to this population. Partnering with SSPs and providing follow up through telemedicine will create an innovative and much-needed opportunity to provide evidence-based prevention strategies for a difficult-to-reach population.

2. Purpose and study objectives

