The **purpose** of this study is to provide medication for opioid use disorder (MOUD) with buprenorphine and naloxone, or bup/nx, and pre-exposure prophylaxis (PrEP) for HIV prevention for persons who inject opioids accessing syringe services programs (SSPs), as part of a comprehensive harm reduction program, and assess the acceptability and feasibility of using telemedicine to implement the program.

The initial visit will be conducted either in person or remotely via telemedicine given COVID-19 protocols at the SSP sites in Charlotte and Wilmington; follow-up visits will be conducted via telemedicine. The study will include a site coordinator at each site and a central study coordinator. The site coordinators will be trained phlebotomists, responsible for follow-up visit scheduling and coordination, and collection of urine and blood samples. The central study coordinator will be responsible for participant screening, formal consenting, and collection of baseline and follow up participant questionnaires.

The **study objectives** are the following:

- a) To assess uptake and persistence to bup/nx and PrEP as part of a comprehensive harm reduction program among people who inject drugs using SSPs.
- b) To assess feasibility and acceptability of implementing a telemedicine-based MOUD and PrEP program among program implementers
- c) To assess feasibility and acceptability of participating in a telemedicine-based MOUD and PrEP program among users (*this objective will be assessed in an ancillary protocol*)

3. Study population and setting

The study population is people who inject drugs, specifically opioids, and who access services at SSPs. The settings is the SSP sites in Wilmington in New Hanover County and Charlotte in Mecklenburg County.

4. Study design

We plan to enroll 20 PWID (10 at each site) accessing the participating SSP sites in Charlotte and Wilmington, NC. Participants will be enrolled in the study for 6 months. At the end of the study, they will be referred to MOUD and PrEP providers identified in the community.

5. Eligibility, sample size, recruitment, and data collection

P2

Providing comprehensive harm reduction via telemedicine for PWID using syringe services programs: a feasibility study

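### Item 3b compares paired with individual treatment, but single-drug status arises only after entry, so the natural comparisons cannot show whether pairing helps persistence

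*Combined protocol and SAP*

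**What the plan says.** Section 6 (Data analysis) ends with a list of what the study hopes to determine. Item 3 concerns retention or persistence. Item 3a takes the proportion still on treatment at Month 3 and Month 6, with a bracket naming MOUD, PrEP or both. Item 3b adds: "We will also examine whether participants are more apt to remain on paired/combined therapy compared to individual treatment". It does not define the two groups, when membership is fixed, what counts as remaining, or a method. The only method that Section 6 gives for Objective 1 is descriptive statistics of baseline characteristics.

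Other parts of the document determine who can be in each group:

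- Section 1: "we will provide both PrEP and MOUD for PWID utilizing SSPs in New Hanover and Mecklenburg counties".
- Section 2, objective (a): "To assess uptake and persistence to bup/nx and PrEP". Uptake is therefore an outcome in its own right.
- Section 5, Eligibility: participants must be "willing to take bup/nx and PrEP for 6 months", and "participants must not currently be taking PrEP or any form of MOUD".
- Section 5, Sample size: a participant who stops one drug of the pair may stay on study. If someone drops out, "we will consider enrolling another participant to fill the spot".
- Schedule of study activities, Week 1: prescriptions are sent and medication begins.

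**The concern.** A comparison of paired with individual treatment needs people whose treatment is individual for some reason other than the outcome. Here nobody enters on one drug and nobody is assigned to one. A participant becomes single-drug by stopping a drug or never starting it, by choice or through access. Under Medications in Section 5, PrEP comes through insurance or an assistance program and bup/nx is collected weekly. Description of Potential Risks lists loss of access among the causes of abrupt bup/nx discontinuation. The comparator is thus partly defined by persistence itself.

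At stake is a report that participants stay better, or worse, on paired therapy when the direction came from the definition chosen or from who had already stopped. A second, smaller matter is that item 3a can be read as one pooled figure. That figure would not show which drug was stopped, although objective (a) names both drugs.

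**Working it through.** **Inputs.** From the documents: 10 participants at each of two sites, so 10 × 2 = 20, which reproduces the stated total. They give no persistence rates, effect size or test for 3b. Every rate below is therefore an assumption, and pairing has no effect in any of these calculations.

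**Reading (i): on both v on each drug.** Being on both implies being on each, so P(both) ≤ min{P(MOUD), P(PrEP)}. With assumed proportions of 0.7 and 0.4, P(both) lies between 0.7 + 0.4 − 1 = 0.10 and 0.40. The direction is fixed by logic and needs no assumption.

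**Reading (ii): on both v on exactly one.** With persistence p on each drug and independent drugs, the proportions are p² and 2p(1 − p). They are equal when p = 2(1 − p), that is at p = 2/3. Expected numbers of 20:

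| p | both, 20p² | exactly one, 40p(1 − p) |
|---|---|---|
| 0.5 | 5.0 | 10.0 |
| 0.6 | 7.2 | 9.6 |
| 0.7 | 9.8 | 8.4 |
| 0.8 | 12.8 | 6.4 |

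The sign follows the overall level of persistence (and, if the drugs are not independent, their overlap).

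**Reading (iii): groups by Month 3 status, followed to Month 6.** Let q be the continuation per drug from Month 3 to Month 6, the same for everyone, with independent drugs.

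- If remaining means keeping every drug held at Month 3: both q², one q. The difference is −q(1 − q).
- If remaining means being on any drug: both 1 − (1 − q)², one q. The difference is +q(1 − q).

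| q | keep all: both v one | any drug: both v one | difference (points) |
|---|---|---|---|
| 0.5 | 25% v 50% | 75% v 50% | ∓25 |
| 0.7 | 49% v 70% | 91% v 70% | ∓21 |
| 0.9 | 81% v 90% | 99% v 90% | ∓9 |

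The same data support opposite statements.

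**Reading (iii), counted per drug, with people who differ.** Half the cohort has continuation q₁ per three months and half q₂. All start both drugs, q is the same in Months 0–3 and 3–6, and the drugs are independent within each half. Continuation per drug from Month 3 to Month 6 is:

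- both group: Σq³ / Σq²
- single-drug group: Σq²(1 − q) / Σq(1 − q)

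| q₁ / q₂ | both | one | gap (points) |
|---|---|---|---|
| 0.80 / 0.60 | 0.728/1.000 = 72.8% | 0.272/0.400 = 68.0% | 4.8 |
| 0.85 / 0.55 | 0.7805/1.025 = 76.1% | 0.2445/0.375 = 65.2% | 10.9 |
| 0.90 / 0.50 | 0.854/1.060 = 80.6% | 0.206/0.340 = 60.6% | 20.0 |

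In the last row the expected groups are 20 × 1.06/2 = 10.6 on both, 20 × 0.34 = 6.8 on one and 2.6 on neither. The gap comes only from who had already stopped a drug by Month 3.

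**The case against.** The strongest reply is that 3b is an exploratory sub-item in a 20-person feasibility study. It names no test, sets no decision rule and claims no causal effect. In a cohort offered both drugs, its plainest meaning may be descriptive: do people stay on both or drop to one? Much of this stands. That count is supportable and worth reporting, and it is why the point is minor. But 3b is worded as a comparison, and followed as written it can yield a directional statement with no effect of pairing behind it.

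A reader might infer more than the documents support:

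- *That the plan commits to a causal analysis of pairing.* It does not; 3b only says the question will be examined.
- *That no analysis of the two drugs together could be informative.* The three readings above are the natural ones, not an exhaustive list. Whether stopping one drug goes with stopping the other could be described, though it would be confounded in the same way.
- *That item 3a certainly pools the drugs.* Its bracket may simply list categories, and Section 5 plans adherence evaluation for each drug. Pooling is one possible reading.
- *That the numerical gaps estimate a bias.* They are illustrations. The ±q(1 − q) swing is algebra, the 20-point gap needs a wide assumed mix, and the mixes set aside participants who never start a drug.

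**Conclusion.** The point holds in a limited form. The cohort has no entry-defined individual-treatment group, and the natural comparisons under 3b do not show whether pairing helps persistence. Two parts of this need no assumed rates: single-drug status is post-entry, and P(both) cannot exceed P(either drug). The sizes rest on assumed rates and on independence of the drugs: a 21-point deficit or advantage at 70% continuation, depending on the definition, and a per-drug gap from 4.8 to 20.0 points from differences between people. Severity is minor. The main feasibility aims are not affected, and nothing here suggests that the planned counts by drug are unsound.

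**What to change.** **Item 3b.** Replace the comparative wording with a descriptive table at Month 3 and Month 6: number on both, MOUD only, PrEP only and neither. For each drug, separate never-started from stopped. Give withdrawn participants and those still enrolled but not assessed their own rows. State that no conclusion about the effect of pairing will be drawn.

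**Item 3a.** Report MOUD persistence and PrEP persistence separately, each with an exact 95% CI. Use the adherence questionnaire planned for Months 3 and 6 (Section 5, Follow up visits), supported for bup/nx by the urine result where one is given (Section 8, Study Monitoring).

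**Denominator.** Item 3a names none, although consent comes before the laboratory results that can exclude a participant, and leavers may be replaced. Use all who consented and remained eligible after the baseline labs, including replaced participants and their replacements.

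**Withdrawn and unassessed.** Count withdrawn participants as not retained in the program. This is a statement about retention, not about drug use: on withdrawal for pregnancy the plan is to "link the pregnant woman to PrEP and MOUD services in the community without lapse". On incarceration the team will "cease any ongoing study activities, including ongoing data collection", and the table needs nothing after that point. Apply a none-to-all range only to participants still enrolled but not assessed. As an assumed example, take 22 eligible (20 plus 2 replacements): 10 on the drug, 8 off, 2 withdrawn and 2 unassessed. The range runs from 10/22 = 45.5% (exact 95% CI 24.4–67.8%) to 12/22 = 54.5% (32.2–75.6%, the mirror image of the first interval).

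**Cost.** SAP wording and one table, from measurements already planned. If the questionnaire does not already ask whether each drug was ever started, that item is needed. The paired-versus-individual comparison is given up, self-report misses non-attenders, and intervals stay wide with about 20 participants (10/20 has an exact 95% CI of 27.2–72.8%).
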